## **Statistical Analysis Plan (SAP) for STARS ("STudy of Alteplase for Respiratory failure in SARS-Cov2 (COVID-19)": A Phase 2a Clinical Trial**

This SAP follows the recently published Guidelines for the Content of Statistical Analysis Plans in Clinical Trials. 

### **Section 1: Administrative Information**

**1a Title:** STARS ("STudy of Alteplase for Respiratory failure in SARS-Cov2 (COVID-19)")

**1b Trial registration number:** NCT

**2. SAP version 4, 11/30/2020**

### **Section 2: Introduction**

#### **2.1. Synopsis of trial background and rationale**

Similar to pathologic findings of ARDS, microthrombi have now been observed in lung specimens from patients infected with COVID-19 . Generalized derangements of the hemostatic system with prolongation of the prothrombin time, reduced prothrombin time activity, and elevated D-dimer and fibrin degradation products have been reported in severely ill COVID-19 patients, particularly in non-survivors . These laboratory findings, in combination with the large clot burden seen in the pulmonary microvasculature, mirrors that seen in human sepsis , experimental endotoxemia , and massive tissue trauma . Targeting the coagulation and fibrinolytic systems to improve the treatment of ARDS has been proposed for at least the past two decades . In particular, the use of plasminogen activators to limit ARDS progression and reduce ARDS-induced death has received strong support from animal models , and a phase 1 human clinical trial . In 2001, Hardaway and colleagues  showed that administration of either urokinase or streptokinase to patients with terminal ARDS reduced the expected mortality from 100% to 70% with no adverse bleeding events.

Tissue plasminogen activator (alteplase) is a more modern approach to fibrinolysis, for which there is extensive experience in myocardial infarction, stroke and major pulmonary embolism . Most current trials included in clinicaltrials.gov for the COVID-19-induced SARS aim at modulating the inflammatory response or test anti-viral drugs. Sarilumab and tocilizumab that block IL-6 effects are being tested in RCT for patients hospitalized with severe COVID-19 (NCT04317092, NCT04322773, NCT04327388). The World Health Organization international trial SOLIDARITY will test remdesivir; chloroquine + hydroxychloroquine; lopinavir + ritonavir; and lopinavir + ritonavir and interferon-beta (NCT04321616). Yet studies targeting the coagulation system, which is intrinsically intertwined with the inflammatory response are lacking. 

Alteplase is already being used in several centers off label for salvage therapy in patients with severe COVID-19 induced SARS (SARS-Cov2) with promising results. These investigators recognize that in the context of a pandemic with no known treatment, it is important to have a

rigorous yet efficient study design with a control group. Thus, we propose a Phase 2a, open label, rapidly adaptive, randomized trial to test the use of two doses of alteplase followed by heparin compared to controls receiving standard of care.

***We hypothesize that administration of tPA to patients with COVID-19 associated severe ARDS will improve pulmonary gas exchange and oxygenation via a decrease in pulmonary vascular microthrombi.***

## 2.2 Outcomes

**Primary Outcome:** PaO2/FiO2 improvement from pre-to-post intervention at 48 hours post randomization. The 48 hours PaO2/FiO2 should ideally be obtained in the same position and the same dose of paralytic agents as in baseline, however, given the pragmatic nature of the trial, this decision must be made by the care team. The 48 hours post-randomization outcome PaO2/FiO2 will be measured under the optimal ventilation strategy within 42 to 54 hours (48 hours +/- 6 hours) post randomization.

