studies by Hardaway et al evaluating fibrinolytic therapy for treatment of ARDS used urokinase and streptokinase, the more contemporary approach to thrombolytic therapy involves the use of tissue-type plasminogen activator (tPA) due to higher efficacy of clot lysis with comparable bleeding risk to the other fibrinolytic agents.

Hypothesis:

We hypothesize that administration of tPA to patients with COVID-19 associated severe ARDS will improve pulmonary gas exchange and oxygenation via a decrease in pulmonary vascular microthrombi.

Study Design:

This is a Phase IIa clinical trial, open label, with a modified stepped-wedge design, testing systemic administration of fibrinolytic therapy with alteplase (tPA) versus standard of care for patients infected with COVID-19 resulting in severe respiratory failure. The design is a rapidly adaptive, pragmatic clinical trial, with 3 interim analyses and 1 final look at the data. Pre-planned adaptations described below will be contemplated at each interim analysis or earlier if recommended by the Data Safety Monitoring Board (DSMB).

Inclusion Criteria: We will include adult patients ages 18-75 years old with known or suspected COVID-19 infection with a PaO₂/FiO₂ ratio < 150 or inferred PaO₂/FiO₂ ratio from SpO₂ if ABG is unavailable (Table) persisting for > 4 hours despite optimal mechanical ventilation management according to each institution's ventilation protocols, and a neurological exam without focal signs or new deficits at time of enrollment (if patient is on paralytics, patient has been aroused sufficiently to allow a neurological examination to exclude new focal deficits or has MRI/CT scan in the last 4.5 hours with no evidence of stroke. Finally, patients must be on the ventilator for ≤10 days to be eligible. Based on experience with critically ill patients, longer ventilation time may be associated with increased risk of bleeding. Patients will be enrolled based on clinical features, without consideration of language (using hospital interpreters and translated consent), race/ethnicity, or gender. A neurological exam or CT/MRI scan to demonstrate no evidence of an acute stroke is needed due to a recent case-report of large-vessel stroke as a presenting feature of COVID-19 in young individuals.⁴⁴

SPO2	FIO2														
	0.3	0.35	0.4	0.45	0.5	0.55	0.6	0.65	0.7	0.75	0.8	0.85	0.9	0.95	1
80%	148	127	111	98	89	81	74	68	63	59	55	52	49	47	44
81%	151	129	113	101	91	82	76	70	65	60	57	53	50	48	45

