- Heparin dosing for the tPA50 group and for after the 48mg tPA drip in the tPA50 drip group:** An infusion of unfractionated heparin infusion will be continued for up to 7 days or until the patient is extubated and has an O₂ requirement of ≤ 4L/min by nasal cannula, and titrated to maintain the activated partial thromboplastin time to 60-80sec (2.0 to 2.5 times the upper limit of normal) per attending's discretion. In case an additional tPA (alteplase) infusion is needed, the heparin drip should be stopped two hours before and re-started after the alteplase infusion ends, at the same dose as before the alteplase. The goal of this treatment is to prevent recurrent microvascular thrombotic hypoxemia or macrovascular complications (stroke, myocardial infarction or venous thromboembolism) due to possible rebound tPA effects causing hypercoagulability. Intravenous heparin is currently a standard of care (SOC) for COVID-19 patients in the ICU due to their extreme hypercoagulability.

Laboratory Measurements:

1. Arterial blood gases, fibrinogen and D-Dimer levels, PT/INR, aPTT, and CBC. Interval for measurement: before and after tPA IV bolus, 6 hours after the start of the infusion, then every 6 hours for first 24 hours, and once a day for 6 days following treatment intervention in all the groups.
2. Thrombelastography or ROTEM (where available) Interval for measurement: Before and after tPA bolus, 6 hours after the start of the infusion, and every 6 hours for the first 24 hours, then daily thereafter for 6 days or until discharge
3. Troponin and CRP pre-treatment and at 24 hours post-infusion
4. Total Bilirubin test pre-treatment (for baseline liver function)

Laboratory tests will follow the schedule below:

	ABG	CBC with platelet count	PT/INR	PTT	Fibrinogen	D-dimer	TEG or ROTEM	Troponin	CRP	Total Bilirubin
Pre-Treatment	X	X	X	X	X	X	X	X	X	X
After Treatment	X	X	X	X	X	X	X			
Hour 6	X	X	X	X	X	X	X			
Hour 12	X	X	X	X	X	X	X			
Hour 18	X	X	X	X	X	X	X			
Hour 24	X	X	X	X	X	X	X	X	X	
Hour 48	X	X	X	X	X	X	X			
Hour 72	X	X	X	X	X	X	X			
Hour 96	X	X	X	X	X	X	X			
Hour 120	X	X	X	X	X	X	X			
Hour 144	X	X	X	X	X	X	X			
Hour 168	X	X	X	X	X	X	X			

All patients enrolled in the trial, regardless of randomization group, will follow the above lab testing schedule. Total amount of blood to be collected during 7 days of study is 200mL. We are also planning on using the blood and other tissues leftover after the safety labs (discarded samples) for research purposes.

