Additional two tubes (total volume up to 8.0mL) of blood will be drawn at each timepoint to be processed in the research lab.

Thrombo Therapeutics, Inc. is not involved in this study. TPA-challenged TEG assay is used for research purposes only. The data from this test is not accessible for the clinical care providers and

does not affect the patient care. We are using this assay to study the clot sensitivity and as a marker for hypercoagulability. The results of tPA-challenged TEG assay will not be used for any clinical decision or research subject assignment. At the moment there is no plan to submit tPA-challenged TEG data to the FDA.

Follow-up:

Patients will be followed to death or discharge up to 28 days. Laboratory measurements related to the research study, however, will end at day 7 after randomization.

Outcomes:

Primary Outcome: PaO₂/FiO₂ improvement from pre-to-post intervention at 48 hours post randomization. Ideally, the PaO₂/FiO₂ will be measured with the patient in the same prone/supine position as in baseline, as change in positions may artificially reduce the improvement attributable to the study drug. However, given the pragmatic nature of the trial, the prone/supine position will be determined by the attending physician, in which case, we will use as an outcome the PaO₂/FiO₂ closest to the 48 hours obtained prior to the change in position as the outcome.

Secondary outcomes (assessed 48 hours after randomization or as indicated):

- PaO₂/FiO₂ improvement from pre-to-post intervention at **24 hours** post randomization.
- Amendment Nov 5, 2020: add the outcome "Decrease in ventilatory dead space as estimated by the ventilatory ratio at **48 hours.**" Based on a recent study, (Orfanos S, El Hussein I, Nahass T, et al. Observational study of the use of recombinant tissue-type plasminogen activator in COVID-19 shows a decrease in physiological dead space. ERJ Open Res 2020; 6: 00455-2020), this outcome seems to appropriate to assess the efficacy of the intervention. As most of the subjects do not have capnography data, we will be using the ventilatory ratio, which has been shown to correlate well with dead space.
- Achievement of PaO₂/FiO₂ ≥ 200 or 50% increase in PaO₂/FiO₂ (whatever is lower)
- National Early Warning Score (NEWS2): based on 7 clinical variables (respiration rate, oxygen saturation, any supplemental oxygen, temperature, systolic blood pressure, heart rate, level of consciousness).

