- NIAID ordinal scale: The ordinal scale is an assessment of the clinical status as follows: 1) Death; 2) Hospitalized, on invasive mechanical ventilation or extracorporeal membrane oxygenation (ECMO); 3) Hospitalized, on non-invasive ventilation or high flow oxygen devices; 4) Hospitalized, requiring supplemental oxygen; 5) Hospitalized, not requiring supplemental oxygen - requiring ongoing medical care (COVID-19 related or otherwise); 6) Hospitalized, not requiring supplemental oxygen - no longer requires ongoing medical care; 7) Not hospitalized, limitation on activities and/or requiring home oxygen; 8) Not hospitalized, no limitations on activities. (combined items 7 and 8 as our study is limited to hospital)

- 48 hour in-hospital mortality
- 14 days in-hospital mortality
- 28 days in-hospital mortality
- ICU-free days (up to 28 days)
- In-hospital coagulation-related event-free (arterial and venous) days (up to 28 days)
- Ventilator-free days (up to 28 days)
- Successful extubation (no re-intubation for >3 days after initial extubation)
- Successful weaning from paralysis for > 3 days after initial termination
- Survival to discharge

Sample size and Power Analysis: (Pass, 14.0, NCSS, LLC, Kaysville, Utah, USA)

We anticipate that each of the five centers will enroll 8-12 patients. Sample size and power Analysis was conducted using Pass, vs 14.0 (NCSS, LLC, Kaysville, Utah, USA) and focused on the primary outcome as defined above. Sample size assumptions:

- power=80%, confidence=95%, and 4 sequential tests(3 interim+1 final), using the Pocock spending function to determine test boundaries,
- potential improvement assumptions based on a previous study ⁴⁰ with appropriate(e.g., Denver) altitude correction as well as mean baseline PaO₂/FiO₂=149 with an overestimated standard deviation of 100,
- design effect=1.12 due to the study's multicenter nature (intra-class correlation coefficient=0.03, average cluster=5);
- ~20% inflation to account for premature death

A sample size of 50 (25 in each intervention group and 25 in the control group) patients detects a >70% improvement in PaO₂/FiO₂ between intervention groups (both tPA50 and tPA 50 plus drip) and controls, and >91% improvement in PaO₂/FiO₂ between intervention tPA 50 plus drip) and controls. Recruitment will assume at least 30% increase to account for refusal or inability to consent.

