### Section 3: Study Methods

**3.1. Trial design** Multicenter, pragmatic, randomized, open label, rapidly adaptive, controlled, clinical trial

The trial has a novel design with modified stepped-wedge and adaptive features in order to rapidly identify the intervention group with the highest chance of benefit. This unconventional design is appropriate for the current circumstances of the pandemic caused by a new, lethal and morbid virus infection (COVID-19) for which no known treatment exists. The below figure illustrates the design. In brief, the patients will be sequentially assigned to one of three following groups:

[figure not shown]
[figure not shown]
- Group tPA50 will receive 50 mg of tPA intravenous bolus administration over 2 hours, given as a 10 mg push followed by the remaining 40 mgs over a total time of 2 hrs (not to exceed 0.9mg/kg dose). Immediately following the tPA infusion, 5000 U of UFH will be delivered and the heparin drip will be continued to maintain the activated partial thromboplastin time at 60-80sec (2.0 to 2.5 times the upper limit of normal). This tPA protocol is a modification of the GUSTO I to III trials. 44,45
- Group tPA50 plus drip will receive 50 mg of tPA intravenous bolus administration over 2 hours, given as a 10 mg push followed by the remaining 40 mgs over a total time of 2 hrs (not to exceed 0.9mg/kg dose). Immediately following this initial tPA infusion, we will initiate a drip of 2 mg/hr tPA over the ensuing 24 hours (total 48 mg infusion) accompanied by an infusion of 500 U/hr heparin during the tPA drip. After this, heparin dose will be increased slowly to maintain a PTT between 60 and 80 sec, titrated per attending's discretion.
- Control: institution's protocol for ARDS

In order to rapidly accrue patients in one intervention group with a concurrent control, the first 10 patients will be randomly assigned to Group tPA50 or Control (Standard-of-care) when the first interim analysis occurs. If no stopping criteria are met, the next 10 patients are randomly

assigned to Group tPA50 or Control when the second interim analysis is done. If no criteria for stopping or dropping an arm are met, the next 10 patients are randomly assigned to Group tPA50 plus drip or Control when the third interim analysis is done. Finally, if no criteria for stopping or dropping an arm are met, the trial progresses with patients being randomized to Group tPA50 plus drip or Control up to the final analysis at n=50.

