### 3.2. Sample size

We anticipate that each of the five centers will enroll 8-12 patients. Sample size and power Analysis was conducted using Pass, vs 14.0 (NCSS, LLC, Kaysville, Utah, USA) and focused on the primary outcome as defined above.

Sample size assumptions:

- power=80%, confidence=95%, and 4 sequential tests(3 interim+1 final), using the Pocock spending function to determine test boundaries,
- potential improvement assumptions based on a previous study 40 with appropriate(e.g., Denver) altitude correction as well as mean baseline PaO2/FiO2=149 with an overestimated standard deviation of 100,
- design effect=1.12 due to the study's multicenter nature (intra-class correlation coefficient=0.03, average cluster=5);
- ~20% inflation to account for premature death

---

 Urbaniak, G. C., & Plous, S. (2013). Research Randomizer (Version 4.0) [Computer software]. Retrieved on April 10, 2020, at <http://www.randomizer.org/>

A sample size of 50 (25 in each intervention group and 25 in the control group) patients detects a >70% improvement in PaO2/FiO2 between intervention groups (both tPA50 and tPA 50 plus drip) and controls, and >91% improvement in PaO2/FiO2 between intervention tPA 50 plus drip) and controls. Recruitment will assume at least 30% increase to account for refusal or inability to consent.

**Consent: We anticipate consenting enough patients to result in 50 eligible patients, thus we plan on a max of 60, to be re-evaluated during each of the interim analyses. LAR, as defined by the state and institutions legislation/policies, will be able to consent.**

The table below shows the details of the interim analyses with the Pocock spending method:

Look	N of Patients	Lower Bndry	Upper Bndry	Nominal Alpha	Inc Alpha	Total Alpha	Inc Power	Total Power
1	10	-2.43798	2.43798	0.015	0.015	0.015	0.18976	0.190
2	20	-2.42677	2.42677	0.015	0.011	0.026	0.25179	0.442
3	30	-2.41014	2.41014	0.016	0.009	0.035	0.21191	0.653
4	50	-2.39658	2.39658	0.017	0.008	0.043	0.14655	0.800

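### The SAP gives a 42–54 h window and an undefined ventilation condition for the primary P/F, but no general rule for which gas counts

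*SAP*

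**What the plan says.** SAP 2.2 (Outcomes) defines the primary outcome as the improvement in P/F from before to after the intervention, at 48 hours from randomization. The outcome value "will be measured under the optimal ventilation strategy within 42 to 54 hours (48 hours +/- 6 hours) post randomization". The same paragraph prefers the baseline position and paralytic dose, but "given the pragmatic nature of the trial, this decision must be made by the care team". Neither document defines the ventilation condition for the outcome gas, says who judges it, or names the value to use when several gases fall in the window.

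The trial is open label in both documents: "This is a Phase IIa clinical trial, open label, with a modified stepped-wedge design" (Protocol, Study Design) and "Multicenter, pragmatic, randomized, open label, rapidly adaptive, controlled, clinical trial" (SAP 3.1). Neither describes blinded selection of the gas.

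Two protocol provisions bear on this:

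- **Schedule.** The table under Laboratory Measurements has one arterial gas at Hour 48, with neighbours at Hours 24 and 72. It adds: "All patients enrolled in the trial, regardless of randomization group, will follow the above lab testing schedule".
- **Position change.** Under Outcomes, if the attending physician changes the patient's position, the outcome is the P/F "closest to the 48 hours obtained prior to the change in position as the outcome". The SAP does not repeat this rule, and the protocol does not state the ±6 h window.

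**The concern.** If a patient has only the scheduled Hour 48 gas in the window, there is nothing to choose. If further clinical gases are taken between 42 and 54 h, the SAP gives a ventilation condition but no tie-break. Someone must then decide which value met that condition, and in an open-label trial that person may know the assignment. The timing of the gas within the window is open in the same way.

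The two documents can also disagree about a single patient. Suppose position changes at 40 h. The protocol's rule selects a gas taken before 40 h, which the SAP window does not admit.

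This variable carries much of the trial's decision-making. It enters the efficacy stopping criterion (SAP 3.3) and the ≥20% and ≥50% rules after 20 patients (SAP 3.1 and 3.4; Protocol, Adaptive design). It is also tested both between groups and within group as improvement over baseline (SAP 6.4). Selection concentrated in the tPA arm would move the between-group contrast towards benefit with no drug effect. Equal selection in both arms would still inflate within-group improvement.

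**Working it through.** **1. The plan's own figure.** Inputs are "power=80%, confidence=95%, and 4 sequential tests(3 interim+1 final), using the Pocock spending function to determine test boundaries" (SAP 3.2, Sample size), "mean baseline PaO₂/FiO₂=149 with an overestimated standard deviation of 100" (Protocol, Sample size and Power Analysis), design effect 1.12, about 20% deaths, and 25 per arm.

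- Effective n per arm = 25 × 0.8 / 1.12 = 17.86.
- Pocock-type spending at information fractions 0.2, 0.4, 0.6 and 0.8 gives boundaries 2.438, 2.427, 2.410 and 2.397, which match the SAP table. The expected final Z for 80% power is 3.118.
- Detectable difference = 3.118 × 100 × √(2/17.86) = 104.3 points, and 104.3/149 = 70.0%. The stated >70% is reproduced. (With the last look at fraction 1.0 and the printed boundaries it is 104.9 points, or 70.4%.)

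This is context only. The point does not change the sample size.

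**2. Shift from taking the highest of k gases.** The documents give neither the number of gases in the window nor their within-patient SD. Assume k = 2 or 3, SD 20–40 points and independent errors. Shift = E[max of k standard normals] × SD, with E = 0.564 for k = 2 and 0.846 for k = 3.

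**3. Effect on a 5% test.** Assume selection in every tPA patient and no control, no drug effect, 20 per arm and outcome SD 100. The standard error is 100 × √(2/20) = 31.6. The error rate is that of a two-sided t-test with 38 df and non-centrality shift/31.6.

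| k | within-patient SD | shift (points) | % of 149 | two-sided error |
|---|---|---|---|---|
| 2 | 20 | 11.3 | 7.6 | 6.4% |
| 2 | 40 | 22.6 | 15.1 | 10.7% |
| 3 | 20 | 16.9 | 11.4 | 8.2% |
| 3 | 40 | 33.9 | 22.7 | 18.1% |

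Simulation of the same extremes gave about 6.5% to 18%. If gas-to-gas noise is added on top of the SD of 100, the maximum is 17%.

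**4. With the printed Pocock boundaries.** Using 25 per arm, SD 100, fractions 0.2, 0.4, 0.6 and 1.0, and the same one-sided selection, the overall error is 0.045 without selection. It becomes 0.052 (k = 2, SD 15), 0.089 (k = 3, SD 25) and 0.228 (k = 4, SD 40). The last case goes beyond the range in step 2.

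**5. Milder selection.** If a quarter of tPA patients are affected, the error in the step 3 setting is about 5.0–6.1%. If both arms select equally, it stays at about 5%.

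**6. The 20% adaptation rule.** 20% of 149 is 29.8 points. Take 10 patients per arm, SD 100, no true effect, and k = 3 with SD 25 (shift 21.2).

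- Read within the tPA arm: standard error 100/√10 = 31.6. The chance of meeting the rule is P(Z > 29.8/31.6) = 17%, rising to P(Z > 8.6/31.6) = 39%.
- Read between groups, with selection in the tPA arm only: standard error 100 × √(2/10) = 44.7. The chance rises from 25% to P(Z > 8.6/44.7) = 42%.

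The documents do not say which reading applies.

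**The case against.** The strongest reply is that the SAP sentence sets a condition for taking the gas and is not a rule for choosing among gases already taken. It names a time, 48 hours ± 6, as well as a condition. The only decision that it hands to the care team concerns position and paralytic dose. The condition may simply point back to each institution's ventilation protocol, which both documents use for eligibility. The protocol schedules one gas at Hour 48 for everyone, and its position-change rule shows that the sponsor thinks in terms of nearest in time, not highest.

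Much of this stands. A reader might infer that any gas in the window may be used, picked by unblinded staff with the results in front of them. The documents do not say so: they schedule a single Hour 48 gas and describe no retrospective choice.

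What remains is narrower. The laboratory schedule does not name the Hour 48 sample as the primary value. The closest-to-48-hours rule covers position changes only and is missing from the SAP. For a patient whose position never changes and who has extra gases in the window, neither document says which value is analysed, and nothing prevents a choice.

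**Conclusion.** The gap is real and modest. The primary endpoint of an open-label trial has a 12-hour window, an undefined ventilation condition and no general selection rule, and the two documents differ on position change and window.

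The size cannot be established from the documents. On the assumed values (2–3 gases per patient, within-patient SD 20–40), full selection in the tPA arm alone shifts the contrast by about 11–34 points, against a planned detectable difference of about 104. It raises a 5% error to about 6.5–18% at the planned SD of 100. These are upper bounds, not forecasts. With selection in a quarter of tPA patients the error stays near nominal. With equal selection the between-group effect largely cancels, while within-group improvement remains inflated.

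A reader might go further and quote error rates up to 45%. That needs best-of-three selection in every tPA patient, none in controls, and an outcome SD of 60 that the documents do not give; they plan with 100.

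The case for acting rests on the role of this endpoint in stopping and adaptation and on the low cost of closing the gap.

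**What to change.** State in SAP 2.2 that the primary value is the scheduled Hour 48 arterial gas. If that gas is missing, use the arterial gas nearest to 48 h by time stamp within 42–54 h, taking the earlier one if two are equally near. Select it by program from the REDCap time stamps, not by a judgement of ventilation.

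Reconcile SAP 2.2 with the Outcomes section of the protocol, so that one position-change rule and one window apply in both. This step cannot be skipped. Using the scheduled gas whatever the position would silently override the protocol's pre-change rule, so that exception must either be carried into the SAP with its admissible window or be removed by protocol amendment.

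Record ventilator settings and position with the selected gas, for a sensitivity analysis.

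The cost is a short SAP edit, a programmed selection and alignment of the protocol text. N = 50 and the >70% detectable difference do not change. Each patient has one eligible value, so the shift from choosing among gases is zero. The downside is that some values will be taken under less than ideal settings. The rule also does not remove open-label influence on those settings or on position.
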